### 17.1. PEDIATRIC QUALITY OF LIFE (PEDSQL™) GENERIC CORE SCALE, ACUTE VERSION

The PedsQL Generic Core Scale is designed to measures health-related quality of life (HRQoL) in pediatric subjects and adolescents (2-18 years of age). The developmentally appropriate PedsQL Generic Core Scale will be completed by either the parent or legal guardian and subject at the time points.

The Parent Report for Toddlers (ages 2-4) of the PedsQL Generic Core Scale is composed of 21 items comprising 4 dimensions as follows: 1) Physical Functioning (8 items), 2) Emotional Functioning (5 items), 3) Social Functioning (5 items), 4) School Functioning (3 items).

The Child and Parent Reports of the PedsQL Generic Core Scale for Young Pediatric subjects (ages 5-7), Pediatric subjects (ages 8-12), and Teens (ages 13-18) are composed of 23 items comprising 4 dimensions as follows: 1) Physical Functioning (8 items), 2) Emotional Functioning (5 items), 3) Social Functioning (5 items), 4) School Functioning (5 items).

#### 17.1.1. VARIABLES & DERIVATIONS

Items are collected as either a 5-point Likert scale [from 0 (Never) to 4 (Almost always)] or 3-point scale [0 (Not at all), 2 (Sometimes) and 4 (A lot)] are transformed on a scale from 0 to 100. Items are reversed scored and linearly transformed to a 0-100 scale as follows: 0=100, 1=75, 2=50, 3=25, and 4=0. If more than 50% of the items in the defined subscale are missing, the corresponding subscale score should not be computed. If 50% or more items are completed, impute the mean of the completed items in a defined subscale, where mean is calculated as the sum of the items over the number of items answered. If any subscale score is

Document: \\quintiles.net\Enterprise\Apps\sasdata\SASa\sas\Shire\Teduglutide\ZXA48914\Biostatistics\Documentation\SAP\SHP633-303\_SAP\_Draft\_V1.0\_20171023

Author: [REDACTED]

Version Number:

Draft V1.2

Version Date:

16Jan2018

Template No: CS\_TP\_BS016 – Revision 3

Reference: CS\_WI\_BS005

Effective Date: 01May2012

Copyright © 2012 Quintiles Transnational Corp. All rights reserved.

The contents of this document are confidential and proprietary to Quintiles Transnational Corp. Unauthorized use, disclosure or reproduction is strictly prohibited.

missing in the summary score calculation, the summary score will be missing.

- Subscale Scores
  - Physical Functioning
  - Emotional Functioning
  - Social Functioning
  - School Functioning
- Summary Scores
  - Psychosocial Health Summary Score - Sum of the items over the number of items answered in the Emotional, Social, and School Functioning Subscales
  - Physical Health Summary Score - Physical Functioning Subscale Score
  - Total Scores - Sum of all the items over the number of items answered on all the subscales

## **17.2. PEDIATRIC QUALITY OF LIFE (PedsQL™) FAMILY IMPACT MODULE, ACUTE VERSION**

The PedsQL Family Impact Module is a parent-report multidimensional instrument that will be completed by the parent or legal guardian. The PedsQL Family Impact Module is a specific module of the PedsQL that is used to measure the impact of pediatric chronic health conditions on parents and the family. The 36-item PedsQL Family Impact Module consists of 6 scales measuring parent self-reported functioning as follows: 1) Physical Functioning (6 items), 2) Emotional Functioning (5 items), 3) Social Functioning (4 items), 4) Cognitive Functioning (5 items; worries about treatment and disease), 5) Communication (3 items), 6) Worry (5 items). Two additional scales measure parent reported family functioning as follows: 1) Daily Activities (3 items), and 2) Family Relationships (5 items).

### **17.2.1. VARIABLES & DERIVATIONS**

Items are collected as a 5-point Likert scale from 0 (Never) to 4 (Almost always) are transformed on a scale from 0 to 100. Items are reversed scored and linearly transformed to a 0-100 scale as follows: 0=100, 1=75, 2=50, 3=25, and 4=0. If more than 50% of the items in the defined subscale are missing, the corresponding subscale score should not be computed. If 50% or more items are completed, impute the mean of the completed items in a defined

Document: \\quintiles.net\Enterprise\Apps\sasdata\SASa\sas\Shire\Teduglutide\ZXA48914\Biostatistics\Documentation\SAP\SHP633-303\_SAP\_Draft\_V1.0\_20171023

Author: [REDACTED] Version Number: Draft V1.2  
Version Date: 16Jan2018

Template No: CS\_TP\_BS016 – Revision 3  
Effective Date: 01May2012

Reference: CS\_WI\_BS005

Copyright © 2012 Quintiles Transnational Corp. All rights reserved.  
The contents of this document are confidential and proprietary to Quintiles Transnational Corp. Unauthorized use, disclosure or reproduction is strictly prohibited.

subscale, where mean is calculated as the sum of the items over the number of items answered. If any subscale score is missing in the summary score calculation, the summary score will be missing.

- Subscale Scores
  - Physical Functioning
  - Emotional Functioning
  - Social Functioning
  - Cognitive Functioning
  - Communication
  - Worry
  - Daily Activities
  - Family Relationships
- Summary Scores
  - Parent HRQL Summary Score - Sum of the items divided by the number of items answered in the Physical, Emotional, Social, and Cognitive Functioning subscales
  - Family Functioning Summary Score - Sum of the items divided by the number of items answered in the Daily Activities and Family Relationships subscales
  - Total Scores - Sum of all the items over the number of items answered on all the subscales

### **17.3. PedsQL (PedsQL™) GASTROINTESTINAL SYMPTOMS MODULE, ACUTE VERSION**

The PedsQL Gastrointestinal Symptom Module is a disease-specific 58-item module, comprised of 10 different symptom scales that assess gastrointestinal symptom-related quality of life. Only the scales of Food and Drink Limits (6 items) and Diarrhea (7 items) will be collected in this study. The scales will be completed by either the parent or legal guardian and subject.

#### **17.3.1. VARIABLES & DERIVATIONS**

Items are collected as a 5-point Likert scale from 0 (Never) to 4 (Almost always) that are transformed to a 0 to 100 scale. Items are reversed scored and linearly transformed to a 0-100

---

Document: \\quintiles.net\Enterprise\Apps\sasdata\SASa\sas\Shire\Teduglutide\ZXA48914\Biostatistics\Documentation\SAP\SHP633-303\_SAP\_Draft\_V1.0\_20171023

Author: [REDACTED] Version Number: Draft V1.2  
Version Date: 16Jan2018

Template No: CS\_TP\_BS016 – Revision 3  
Effective Date: 01May2012

Reference: CS\_WI\_BS005

Copyright © 2012 Quintiles Transnational Corp. All rights reserved.  
The contents of this document are confidential and proprietary to Quintiles Transnational Corp. Unauthorized use, disclosure or reproduction is strictly prohibited.

scale as follows: 0=100, 1=75, 2=50, 3=25, and 4=0. If more than 50% of the items in the scale are missing, the corresponding scale score should not be computed. If 50% or more items are completed, impute the mean of the completed items in a scale, where mean is calculated as the sum of the items over the number of items answered.

- Symptoms Total Scales Score
  - Food and Drink Limits Scale Score
  - Diarrhea Scale Score

#### **17.4. MISSING DATA METHODS**

Missing item scales will not be imputed. The subscale scores and the total scores will be set to missing if more than 50% of the items in the scale are missing in the scale.

#### **17.5. ANALYSIS OF HRQOL VARIABLES**

Total scores, subscale scores and summary scores will be summarized by study visit and treatment group using descriptive statistics including number of subjects, mean, standard deviation, median, minimum and maximum. Change from baseline by visit will be summarized, with subjects excluded from change from baseline summaries at the visit associated with the subject's baseline measurement.

### **18. SAFETY OUTCOMES**

There will be no statistical comparisons between the treatment groups for safety data.

#### **18.1. ADVERSE EVENTS**

Adverse Events collected during the prospective observation period will be coded using ***Medical Dictionary for Regulatory Activities (MedDRA) central coding dictionary***. Investigator verbatim as well as preferred terms and system organ classes will be included in the listings.

Treatment-emergent adverse events (TEAEs) are defined as adverse events that started or worsened on or after the first dose of teduglutide treatment in the core study TED-C13-003.

See [APPENDIX 2](#) for handling of partial dates for AEs. In the case where it is not possible to

---

Document: \\quintiles.net\Enterprise\Apps\sasdata\SASa\sas\Shire\Teduglutide\ZXA48914\Biostatistics\Documentation\SAP\SHP633-303\_SAP\_Draft\_V1.0\_20171023

Author: [REDACTED] Version Number: Draft V1.2  
Version Date: 16Jan2018

Template No: CS\_TP\_BS016 – Revision 3  
Effective Date: 01May2012

Reference: CS\_WI\_BS005

Copyright © 2012 Quintiles Transnational Corp. All rights reserved.  
The contents of this document are confidential and proprietary to Quintiles Transnational Corp. Unauthorized use, disclosure or reproduction is strictly prohibited.

define an AE as treatment-emergent or not, the AE will be classified by the worst case (i.e. treatment-emergent).

An overall summary of number of subjects within each of the categories described below will be provided as specified in the templates. Adverse events will be summarized using descriptive statistics (e.g., number and percentage of subjects). The number of events will also be presented except for summaries by highest category. The summary will include any TEAE, severity of TEAEs (highest category), investigator assessment of relationship of TEAEs to study drug, treatment-emergent serious AEs (TESAEs), investigator assessment of relationship of TESAEs to study drug, TEAEs leading to study drug discontinuations, TEAEs leading to study discontinuations and TEAEs leading to death for both TED and NNT cycles. Adverse events will be summarized for treatment cycles and no treatment periods, and for the entire on study time interval as well.

Listings will include both TEAEs and Non-TEAEs (unless specified otherwise and excluding adverse events which began during the core study that did not worsen after the start of this study) and will be provided for serious adverse events, adverse events leading to death, adverse events leading to discontinuation of study drug, adverse events leading to discontinuation of study and adverse events of special interest. Listings will indicate whether an AE is treatment emergent or not. Information for adverse events that satisfy the dose interruption criteria of CTCAE Grade 3 and 4 will only be presented in the listings.

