## 6. ANALYSIS SETS

Analysis of efficacy and safety endpoints will be performed based on the analysis sets defined in this section and as specified for each endpoint throughout this SAP.

Subjects will be classified in treatment groups based on whether they received teduglutide in the core study TED-C13-003 (as 0.0125 mg/kg/day, 0.025 mg/kg or 0.05 mg/kg) and/or during the prospective observation period in this study:

- TED/NTT – includes subjects who took teduglutide in the core study but not in the extension study;
- TED/TED – includes subjects who took teduglutide in the core study and in the extension study;
- ANY TED – includes subjects who took teduglutide in either the core study or in extension study.

No treatment-naïve patients in core study TED-C13-003 enrolled in the extension study SHP633-303, so the treatment groups associated with the NTT in the core study are removed from the statistical analysis.

---

Document: \\quintiles.net\Enterprise\Apps\sasdata\SASa\sas\Shire\Teduglutide\ZXA48914\Biostatistics\Documentation\SAP\SHP633-303\_SAP\_Draft\_V1.0\_20171023

Author: [REDACTED] Version Number: Draft V1.2  
Version Date: 16Jan2018

Template No: CS\_TP\_BS016 – Revision 3  
Effective Date: 01May2012

Reference: CS\_WI\_BS005

Copyright © 2012 Quintiles Transnational Corp. All rights reserved.  
The contents of this document are confidential and proprietary to Quintiles Transnational Corp. Unauthorized use, disclosure or reproduction is strictly prohibited.

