# 7. GENERAL CONSIDERATIONS

## 7.1. REFERENCE START DATE AND STUDY DAY

Study Day will be calculated from the reference start date, and will be used to show start/stop day of assessments and events. In addition, Day of Teduglutide Treatment will be calculated from the date of first dose of Teduglutide following signing of informed consent for the core study.

Reference start date of prospective period is defined as the start of the first cycle within the study, either treatment on Cycle 1 Day 1 for the teduglutide treatment period or the first date of the NTT period of SHP633-303. Note that the reference start date of core study TED-C13-003 is defined as the baseline visit of the extension study SHP633-303 for the efficacy variables. Study days before the reference start date will be negative.

If the date of the event is on or after the reference start date then:

$$\text{Study Day} = (\text{date of event} - \text{reference start date}) + 1.$$

If the date of the event is prior to the reference start date then:

$$\text{Study Day} = (\text{date of event} - \text{reference start date}).$$

In the situation where the event date is partial or missing, the date will appear partial or missing in the listings, and Study Day will be missing.

---

Document: \\quintiles.net\Enterprise\Apps\sasdata\SASa\sas\Shire\Teduglutide\ZXA48914\Biostatistics\Documentation\SAP\SHP633-303\_SAP\_Draft\_V1.0\_20171023

Author: [REDACTED]

Version Number:  
Version Date:

Draft V1.2  
16Jan2018

Template No: CS\_TP\_BS016 – Revision 3

Reference: CS\_WI\_BS005

Effective Date: 01May2012

Copyright © 2012 Quintiles Transnational Corp. All rights reserved.

The contents of this document are confidential and proprietary to Quintiles Transnational Corp. Unauthorized use, disclosure or reproduction is strictly prohibited.

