## APPENDIX 2. PARTIAL DATE CONVENTIONS

Imputed dates will NOT be presented in the listings. The reference start date for adverse events (excluding those events entered as part of the medical history) will be the first teduglutide dose date, if the subject entered a teduglutide treatment period during the study, otherwise the start date of the first non-teduglutide period. The reference start date for medications will be the informed consent date. The reference end date will be the EOS date.

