		month and year of the informed consent: Impute start date as the informed consent date if AE start year and month < the year and month of the reference start date; Else if AE start year and month are known and are not the month and year of the reference start date or informed consent: Impute start date as the first day of the month; Else if only AE start year is known and is the year of the reference start date: Impute start date as the reference start date; Else if only AE start year is known and is after year of the reference start date: Impute start date as the first day of the year (1 st January). If AE stop date is unknown leave as missing.
Missing	Known	If AE start date is unknown leave as missing; event will be considered treatment-emergent if stop date >= the reference start date.
	Partial	If AE start date is unknown leave as missing; event will be considered treatment-emergent if stop date partial stop date >= same partial portions of the reference start date
	Missing	If AE start or stop date is unknown leave as missing; event will be considered treatment-emergent.

Document: \\quintiles.net\Enterprise\Apps\sasdata\SASa\sas\Shire\Teduglutide\ZXA48914\Biostatistics\Documentation\SAP\SHP633-303\_SAP\_Draft\_V1.0\_20171023

Author: [REDACTED] Version Number: Draft V1.2  
Version Date: 16Jan2018

Template No: CS\_TP\_BS016 – Revision 3  
Effective Date: 01May2012

Reference: CS\_WI\_BS005

Copyright © 2012 Quintiles Transnational Corp. All rights reserved.  
The contents of this document are confidential and proprietary to Quintiles Transnational Corp. Unauthorized use, disclosure or reproduction is strictly prohibited.

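### Prospective SAP Appendix 2 tests adverse events with a missing start date against a different date from the Section 18.1 anchor, and places partial onsets without using later cycle start dates

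*SAP*

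**What the plan says.** All references are to the prospective SAP (Draft V1.2).

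Section 18.1 defines treatment-emergent events as "adverse events that started or worsened on or after the first dose of teduglutide treatment in the core study TED-C13-003". It sends partial dates to Appendix 2 and adds that, where an event cannot be classified, "the AE will be classified by the worst case (i.e. treatment-emergent". The same section plans event summaries for treatment cycles, for no-treatment periods and for the whole time on study.

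Appendix 2 sets its own reference start date for adverse events. It "will be the first teduglutide dose date, if the subject entered a teduglutide treatment period during the study". No study is named for that dose. Subjects who never entered such a period get a second rule: "otherwise the start date of the first non-teduglutide period". Events entered as medical history are excluded.

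The Appendix 2 table then does two things with that date:

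- **Start missing, stop known:** "event will be considered treatment-emergent if stop date >= the reference start date". A partial stop date gets the same test on its known parts. With both dates missing, "If AE start or stop date is unknown leave as missing; event will be considered treatment-emergent".
- **Start known to the month:** in the month of the reference date, the onset becomes the reference date, subject to a condition on the stop date where one is recorded. In an earlier consent month it becomes the consent date. In any other month it becomes day 1.

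Section 6 says that TED/NTT "includes subjects who took teduglutide in the core study but not in the extension study". Section 7.1 starts the prospective period at "either treatment on Cycle 1 Day 1 for the teduglutide treatment period or the first date of the NTT period", but counts treatment days from the first dose after core-study consent.

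**The concern.** One flag has two anchors. Section 18.1 ties treatment emergence to the first core-study dose, while the missing-start rows of Appendix 2 decide it from a date that is later for some or all subjects. Those rows give a test but no outcome for an event that fails it, and the SAP does not say whether the worst-case rule then applies. Two programmers could flag the same event differently. The flag appears in the listings and drives the event tables.

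The second part concerns where an event is counted. Tables by cycle and untreated period need an onset that falls in the right period, but the imputation knows only one reference date per subject, with consent as a secondary anchor. Neither is the start of a later cycle.

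Long-term safety is the primary objective and the interim analysis supports a regulatory submission. In a small, purely descriptive study a single reclassified event is visible in a table cell.

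**Working it through.** The SAP has no figure to reproduce. The check applies the written rules to assumed dates: first core dose 10 Mar 2015, extension consent 9 Jan 2017, first untreated period from 20 Feb 2017 (TED/NTT subject), Cycle 1 Day 1 on 20 Jun 2017, Week 28 on 2 Jan 2018 (196 days later) and Cycle 2 Day 1 on 16 May 2018. None of these dates is in the SAP.

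**Part 1: missing start, known stop**

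Rule in Appendix 2: treatment-emergent if stop ≥ reference date. Rule in Section 18.1: with no start date and a stop on or after the core dose, the event cannot be classified, so worst case makes it treatment-emergent.

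| Subject and reference date | Stop 1 Feb 2017 | Stop 15 Apr 2017 | Stop 15 Jul 2017 | Section 18.1, all three |
|---|---|---|---|---|
| TED/NTT, 20 Feb 2017 | fails | passes | passes | treatment-emergent |
| TED/TED, extension dose 20 Jun 2017 | fails | fails | passes | treatment-emergent |
| TED/TED, core dose 10 Mar 2015 | passes | passes | passes | treatment-emergent |

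The anchors conflict only when the stop falls before the Appendix 2 date. For prospectively collected events the window runs from consent to that date:

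- **TED/NTT:** 0 days if the untreated period opens at screening (screening assumed on the consent date). If it opens at the first NTx visit, which Section 4.1 puts 2 to 12 weeks after screening, the window is 2 × 7 = 14 to 12 × 7 = 84 days.
- **TED/TED, extension reading:** with k full 12-week untreated intervals before treatment, 84k to 84k + 84 days. That is 0 to 84 for k = 0, 84 to 168 for k = 1 and 168 to 252 for k = 2. The SAP does not give k. Section 4.1 lets subjects go to pre-treatment at any point after screening, so k = 0 is allowed.
- **TED/TED, core reading:** no conflict.

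These are lengths of a stop-date window, not counts of events.

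**Part 2: onset known to the month, stop date not limiting**

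| Onset month | Possible days by period | Extension reading | Core reading |
|---|---|---|---|
| Jun 2017 (Cycle 1 starts on the 20th) | 19 untreated, 11 Cycle 1 | 20 Jun, Cycle 1 | 1 Jun, untreated |
| Jan 2018 (Week 28 on the 2nd) | 1 Cycle 1, 30 untreated | 1 Jan, Cycle 1 | 1 Jan, Cycle 1 |
| May 2018 (Cycle 2 starts on the 16th) | 15 untreated, 16 Cycle 2 | 1 May, untreated | 1 May, untreated |

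The January row counts the Week 28 day as untreated; counting it in the cycle gives 2 and 29.

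On either reading, the May onset goes to the untreated period although 16 of 31 possible days lie in Cycle 2. In a 30-day month, a cycle starting on day 2 contains 29/30 = 97% of the days and one starting on day 30 contains 1/30 = 3%, yet the event goes to the earlier period in both cases. Only a cycle starting on day 1 escapes. On the extension reading alone, June and May are treated in opposite ways.

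TED/NTT subjects have no extension cycles, so Part 2 concerns TED/TED only. It leaves the treatment-emergent flag unchanged: every analysed subject was dosed in the core study, so an onset after extension consent already meets Section 18.1.

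**The case against.** The strongest reply is that the flag conflict is largely absorbed. Appendix 2 says when an event is treatment-emergent and never says that a failing event is not. Section 18.1 then sends unclassifiable events to the worst case, which gives the right answer. This is plausible but does not settle the matter. The worst-case rule applies where classification is not possible, and Appendix 2 supplies a test that looks decisive; if every failing event were treatment-emergent anyway, the test would do nothing. What stands is that the defect is an unstated precedence, not a demonstrated wrong result.

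The reply is also right on size. Medical-history events are excluded, and Section 12.1 places events ongoing at core completion there. An affected event must have no start information and a stop inside a window that may be empty. For TED/NTT it is the dates that always differ, not the flag.

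A reader might infer more than the documents support:

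- **That Cycle 1 is handled inconsistently with later cycles in all cases.** This holds only on the extension reading.
- **That average misplacement of about half a boundary month proves the rule faulty.** Any single-date rule does this when the day is unknown.
- **That shifts from follow-up to the treatment part of a cycle distort the tables.** Section 7.4 keeps Weeks 25 to 28 inside the cycle, so by-cycle counts do not move.
- **That safety is biased in a known direction.** The January and May examples move in opposite directions.

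Finally, day-1 imputation is explicit and reproducible, and many plans use something similar. That is fair, but it ignores the later cycle starts on which the planned tables depend.

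**Conclusion.** The point holds as a minor one. For TED/NTT the Appendix 2 test date always differs from the Section 18.1 anchor. For TED/TED it differs only if the extension dose is meant; the condition about entering a treatment period during the study points that way, while the treatment-day count in Section 7.1 keeps the core reading open. The SAP does not say which rule decides a missing-start event that stopped between the two dates, although it counts an event with both dates missing. Period assignment of month-only onsets ignores later cycle starts on either reading.

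The SAP gives no number of incompletely dated events; it is probably small. This is a weakness in classification and reproducibility. The window lengths assume screening at consent and 12-week untreated intervals.

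**What to change.** In Appendix 2:

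1. Judge treatment emergence of missing-start events against the first core-study dose, as in Section 18.1. All three test events above then agree with Section 18.1.
2. State that the worst-case rule of Section 18.1 covers anything still unresolved.
3. Name the study in the phrase on the first dose date.
4. For by-period tables, impute partial onsets from the start dates of the cycles and untreated periods compatible with the known date parts. Where a cycle and an untreated period both fit, and the stop date does not rule the cycle out, assign the event to the teduglutide cycle. Do this alike for every cycle, in line with the worst-case principle, and flag the event in the listing.

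Step 4 is needed separately, because re-anchoring alone still leaves the May 2018 onset at 1 May, before Cycle 2.

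The cost is Appendix 2 wording and modest programming of event dates and period flags. No new data are needed, and the treatment-emergent definition and planned tables stay as they are. The downside is that some events from untreated periods may be counted in a cycle; the listing flag makes these visible.

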### 14.1. ADVERSE EVENTS

Adverse Events collected during the retrospective observation period will be coded using **Medical Dictionary for Regulatory Activities (MedDRA) central coding dictionary, Version 19.1**. Investigator verbatim as well as preferred terms and system organ classes will be included in the listings.

An overall summary of number of subjects within each of the categories described below will be provided as specified in the templates. Adverse events that occurred during the retrospective observation period will be summarized using descriptive statistics (e.g., number and percentage of subjects). The number of events will also be presented except for summaries by highest category. The summary will include any AE, severity of AEs (highest category), investigator assessment of relationship of AEs to teduglutide, SAEs, and investigator assessment of relationship of SAEs to teduglutide.

Listings will include all the AEs and SAEs during the retrospective observation period. The ongoing AEs at the end of TED-C13-003 with the end dates are collected in the CRF and will be

Document: \\quintiles.net\Enterprise\Apps\sasdata\SASa\sas\Shire\Teduglutide\ZXA48914\Biostatistics\Documentation\Protocol\SHP633-303\_Retrospective\_SAP\_Final\_V1.0\_20171013  
Author: [REDACTED] Version Number: Final V1.0  
Version Date: 13Oct2017

Template No: CS\_TP\_BS016 – Revision 3  
Effective Date: 01May2012

Reference: CS\_WI\_BS005

Copyright © 2012 Quintiles Transnational Corp. All rights reserved.  
The contents of this document are confidential and proprietary to Quintiles Transnational Corp. Unauthorized use, disclosure or reproduction is strictly prohibited.

listed only.

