## 3. STUDY OBJECTIVES

### 3.1. PRIMARY OBJECTIVE

The primary objective of the study is to evaluate the long-term safety and tolerability of teduglutide treatment in pediatric subjects with Short Bowel Syndrome (SBS) who completed TED-C13-003.

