## 14. STUDY DRUG EXPOSURE

The overall extent of exposure is defined as the number of days on teduglutide during the core study and prospective observation period combined. Exposure summary will be presented by treatment group (TED/TED, TED/NTT and ANY TED only) as a numeric variable. It will also be categorized and presented in pre-defined groups: 0-<12, 12-<24, 24-<48, 48-<72, 72-<96, 96-<120, 120-<144, 144-<168, >=168 weeks. The overall number of cycles on teduglutide will also be summarized as a numeric variable. Finally, the number of days on teduglutide for each prospective period cycle will be summarized.

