## APPENDIX 1. PROGRAMMING CONVENTIONS FOR OUTPUTS

### SHIRE OUTPUT STANDARDS – TFLs4SHIREFINALV6.0

Outputs will be presented according to Shire output standards document TFLs4ShireFinalV6.0.

General considerations which are applicable to the study are summarized as following:

- **Statistics Presentation**

For the by-time-point tables, the number of subjects at each timepoint (n) represents the number that had a valid result for a given parameter at that timepoint.

The default summary statistics presented in the TFLs4Shire table shells for continuous variables include n, mean, standard deviation, median, minimum, and maximum. For categorical variables, the count (n) and percent (%) are the default statistics; unless otherwise stated or the associated number of subjects for the corresponding time point is provided, the denominator for percentages is N (the number of subjects in the treatment group/analysis set). Note that for any summary by subgroups (e.g., by sex), the denominator is the number of subjects in that subgroup/treatment group/analysis set. For most safety tables, the study teams should use the default statistics; the study team should carefully consider and give sufficient justification prior to requesting the use of other summary statistics. Percentages will be reported to 1 decimal place, except when the percentage equals exactly 100 where it will be displayed as an integer (100). For zero, only count and no percentage will be displayed.

- **Alignment**

Output should be aligned so that in the body of the table, where applicable, text is left-justified within a cell, stats output is aligned centrally within a cell and lined up by decimal point.

Handling of missing values: In listings, missing values for numerical data will be reported as a period “.” and missing values for character data as a blank “ ”. In the summary tables for categorical data, “Missing” will always be displayed as a category to represent missing data, where applicable. The default denominator will be all subjects in the analysis set unless otherwise specified in the SAP. For both tables and listings where there are no observations (and hence there would be no output), the table/listing should be produced with all titles and footnotes as per its shell, but with the text showing no observations in the body of the output.

- **Decimal Places and Rounding Rules**

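### Adverse events in the prospective SAP are shown as subject percentages and event counts with no time at risk, so NTT-period, whole-study and group figures partly reflect length of follow-up

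*SAP*

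**What the plan says.** The prospective SAP, section 3.1, sets the aim: "The primary objective of the study is to evaluate the long-term safety and tolerability of teduglutide treatment in pediatric subjects". Section 18.1 gives the method: "Adverse events will be summarized using descriptive statistics (e.g., number and percentage of subjects", and adds: "The number of events will also be presented except for summaries by highest category". It also sets the periods: "Adverse events will be summarized for treatment cycles and no treatment periods, and for the entire on study time interval as well". Appendix 1 fixes the default: "the denominator for percentages is N (the number of subjects in the treatment group/analysis set".

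Time under observation is described elsewhere in the same SAP:

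- Section 4.1: a teduglutide cycle is planned as 28 weeks, made up of 24 weeks on drug and 4 weeks of follow-up off drug. An NTT period has no set length, because a subject who meets a treatment criterion can leave it at any point.
- Section 14: the number of cycles is a variable to be summarised. Overall exposure adds on-drug days in the core study and the prospective period, and is banded as "0-<12, 12-<24, 24-<48, 48-<72, 72-<96, 96-<120, 120-<144, 144-<168, >=168 weeks". Days on drug in each prospective cycle are also summarised.
- Section 6: TED/TED means any teduglutide in the extension after teduglutide in the core study; TED/NTT means none in the extension.

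The retrospective SAP, section 14.1, takes the same approach: events are "summarized using descriptive statistics (e.g., number and percentage of subjects".

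Neither SAP defines time at risk, an event rate per subject-year or a time-to-first-event summary.

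**The concern.** A percentage of subjects with at least one event, or a raw event count, rises with the time watched even when the underlying rate is constant. Here that time varies between subjects and differs systematically between the states being tabulated. A TED/TED subject can contribute both on-drug and off-drug time to the whole-study table, while a TED/NTT subject contributes only off-drug time. A subject followed for longer also has more opportunity to start teduglutide and so be classed as TED/TED.

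These tables carry the primary objective. Without a time basis, a reader cannot tell whether a higher figure in one state or group reflects more events per unit of time or simply more time. The error can go either way: it can suggest a difference that is not there or hide one that is.

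**Working it through.** The plan gives no event rate, expected follow-up or power for this point, so there is no stated figure to reproduce. The check has three steps.

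**1. Do the exposure summaries supply the missing denominator?** All references are to the prospective SAP.

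| Quantity | What is counted | Where |
|---|---|---|
| Adverse events tabulated | Events collected in the prospective period, on and off drug | 18.1 |
| Overall exposure | On-drug days, core study plus prospective period | 14, 14.1 |
| Exposure per cycle | On-drug days in each prospective cycle | 14 |
| NTT time | Not derived | – |
| 4-week follow-up time | Not derived | – |

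Overall exposure covers a wider calendar window than the events and leaves out off-drug time. Only the per-cycle days line up with the event window, and only for on-drug time.

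**2. How far can follow-up alone move a crude percentage?** Under a constant rate r of first events per subject-year, the proportion with at least one event after w weeks is 1 − exp(−r × w / 52.18). The rates 0.1, 0.5 and 1.0 are assumptions chosen to span a range. The lengths of 24 weeks (the on-drug part of one cycle) and 96 weeks (four times as long) are illustrative.

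| Assumed r | 24 weeks | 96 weeks | Ratio |
|---|---|---|---|
| 0.1 | 4.5% | 16.8% | 3.7 |
| 0.5 | 20.5% | 60.1% | 2.9 |
| 1.0 | 36.9% | 84.1% | 2.3 |

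For r = 0.5: 0.5 × 24 / 52.18 = 0.230 and 1 − exp(−0.230) = 20.5%; 0.5 × 96 / 52.18 = 0.920 and 1 − exp(−0.920) = 60.1%. Expected event counts per subject, at any constant rate, differ by 96 / 24 = 4-fold. A rate per subject-year would be the same at both lengths.

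**3. Can a real difference be hidden?** Suppose the on-drug rate is twice the off-drug rate r, with 24 weeks on drug and 48 weeks off. The exponents are 2r × 24 and r × 48, which are equal, so the crude percentages coincide: 8.8% each at r = 0.1, 36.9% at 0.5 and 60.1% at 1.0. A rate per subject-year would show the ratio of 2.

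**The case against.** The strongest reply is that the plan is descriptive and already limits misreading. Section 18 rules out statistical comparison of groups on safety. Section 7.4 puts treatment-period and NTT data in separate tables, and Appendix 1 shows only TED/TED in treatment-period tables, so those tables have no TED/NTT column to misread. A cycle has a planned length, so by-cycle percentages rest on roughly uniform follow-up. Exposure is tabulated by the same groups. Section 18.1 words its statistics as examples and refers to templates in a separate file that is not shown.

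Much of this stands. A reader might infer that the adverse event tables cannot be interpreted at all; the documents do not support that, for the reasons just given. A reader might also take the top exposure band, 168 weeks or more, as the length of adverse event follow-up and compute a 7-fold spread against 24 weeks (168 / 24). That is not supported either: the bands are display categories for on-drug time and include core-study days, so they are not the event window.

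Two parts of the reply fail. A rate is a description, not a test, so ruling out comparisons does not remove the need for a time basis. The exposure tables give no off-drug time, so the NTT and whole-study figures cannot be put on a time basis from what the text specifies.

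A further limit concerns the retrospective SAP. Its section 4.1 collects nonserious events only if they are related to teduglutide or of special interest. An overall on-drug versus off-drug rate there would compare differently ascertained events and could make off-drug time look safer than it was.

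**Conclusion.** The point holds for the prospective NTT-period tables, the whole-study tables and the reading of TED/NTT against TED/TED. It applies far less to by-cycle percentages. That time at risk is unequal follows from the SAP's own text. The size of the effect does not: it depends on the assumed constant rates and illustrative durations, under which a fourfold difference in follow-up changes the crude percentage by a factor of about 2.3 to 3.7. The plan's text pre-specifies no rate; whether the unseen table shells include one cannot be judged. Nothing here shows that a safety signal has been missed or created. This is a worthwhile, low-cost improvement to the analysis of the primary objective, not a flaw that invalidates it.

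**What to change.** In section 18.1 of the prospective SAP:

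- Define subject-years at risk over the same prospective window as the events, for teduglutide cycles, NTT periods and the whole study. Within cycles, show the 24-week on-drug part and the 4-week off-drug follow-up separately, or state where the follow-up is counted.
- Assign each event by its onset date to the state then in force.
- In the overall, related and serious treatment-emergent tables, keep n (%) and add subject-years, events per subject-year, and subjects with a first event per subject-year. The first-event rate matters because a few children with recurrent events can dominate the total event rate. Present all of this descriptively.

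In the retrospective SAP, limit any such rate to serious adverse events.

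The cost is one new time-at-risk derivation and slightly larger tables. No new data are needed: cycle dates already enter section 14.1, and NTT start and end-of-study dates are already used in Appendix 2. The rates will be imprecise, since about 40 subjects are expected in the extension and some may consent to retrospective collection only.
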